Another critical factor involves neuronal development and microglial function. Excessive glutamate release and the presence of pro-inflammatory cytokines have been documented in post-mortem brains of individuals with Down Syndrome and ASD, leading to impaired inter-neuronal communication and disruption of long-range cortical–subcortical connections. These disruptions are strongly associated with deficits in cognition, social interaction, and sensory integration (Rubenstein & Merzenich, 2003; Courchesne & Pierce, 2005; Geschwind & Levitt, 2007; Belmonte, 2010).

Metabolism

Immune suppression in individuals with Down Syndrome, Autism Spectrum Disorders (ASD), and Attention Deficit Disorder (ADD) predisposes them to recurrent infections of the gastrointestinal tract, respiratory system, and ears. The use of antibiotics further disrupts the gut microbiota, exacerbating dysbiosis. This imbalance promotes *Candida* overgrowth, which contributes to the secretion of immunotoxins, intestinal wall damage, and inhibition of immunoglobulin A (IgA), ultimately leading to increased intestinal permeability (*leaky gut*). In Down Syndrome, intestinal sluggishness caused by hypotonia further prolongs exposure to pathogens.

These intestinal alterations impair secretin production, reducing pancreatic and hepatic enzyme release, and thereby hindering nutrient digestion and absorption. The processing of complex proteins such as casein (milk) and gluten (wheat, barley, rye, oats) is disproportionately affected, leaving peptides only partially digested. These altered peptides can cross compromised intestinal and blood–brain barriers, accumulate in the temporal lobes—critical for language and cognition—and exert opioid-like activity. Such effects contribute to mood instability, sensory alterations, sleep disturbances, respiratory depression, reduced attention, antisocial behaviors, and academic underperformance (Shaw, 2008).

Candida also interferes with carbohydrate metabolism by fermenting sugars, leading to three major outcomes:

1. Reduced ATP production from glycolysis/Krebs cycle, depriving specialized cells (e.g., hepatocytes, neurons, pancreatic beta cells) of energy.
2. Production of pentosidines, accelerating oxidative stress and impairing tissue regeneration.

3. Creation of alcoholic byproducts in the intestine, further damaging mucosa, impairing enzymatic activity, and reducing vitamin B synthesis.

Oxidative Stress and Allergies

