Proteins are essential nutrients, second only to water in abundance in the human body. They are the fundamental components of muscles, vital organs, blood cells, enzymes, and hormones (Herman, 2009). Structurally, proteins are chains of amino acids; there are 20 in total, 9 of which are essential and must be obtained from the diet.

Animal-based proteins typically provide all essential amino acids in balanced proportions, whereas plant-based proteins require careful combination to achieve adequacy. Protein quality is evaluated through indices such as Biological Value (BV) and the Protein Digestibility Corrected Amino Acid Score (PDCAAS), the latter having been the preferred method of assessment by both the FDA and WHO since 1993.

The primary role of protein is to support tissue repair and maintenance. When consumed in excess, protein can also serve as a precursor for energy production through the Krebs cycle (Meléndez-Hevia, Waddell & Cascante, 1996). Conversely, insufficient intake compromises tissue integrity.

In individuals with Down Syndrome, Autism Spectrum Disorders (ASD), or Attention Deficit Disorder (ADD), metabolic deficiencies—including allergies or sensitivities—may impair the hydrolysis of certain animal proteins (such as casein, albumin, and red meat proteins) as well as plant proteins like gluten (Shaw, 2008).

The whey protein incorporated into the T-2 investigational nutritional formulation provides all essential amino acids with high bioavailability and closely resembles the composition of human breast milk, making it highly efficient and particularly beneficial for individuals with intestinal dysbiosis. As a pure whey protein concentrate, it carries no allergenic risk.

Flaxseed

The use of flaxseed as a functional food dates back centuries, particularly in European bread-making traditions. Modern studies in the United States have confirmed its health benefits. Flaxseed varieties suitable for human consumption include brown and golden,

with an average composition of 41% fat, 20% protein, 28% dietary fiber, 7.7% moisture, and 3.4% ash (Morris, 2007).

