Milled golden flaxseed flaxseed provides 1.09 g of dietary fiber per serving, which contributes to improved intestinal motility and helps maintain microbiota balance. Its fatty acid profile ensures the sequential metabolic conversion of oleic acid (omega-9), linoleic acid (omega-6), and alpha-linolenic acid (omega-3) into arachidonic acid, EPA, DHA, and prostaglandins, thereby supporting inflammatory regulation and cerebral blood flow.

Dosage and Administration

Participants will be instructed to take 23 g of the T-2 investigational nutritional formulation, twice daily, dissolved in 250 ml of liquid.

For the study population (Trisomy 21, ASD, and ADD/ADHD), it is recommended that the investigational formulation be prepared with Casein-free beverage, which is casein-free and enriched with probiotic fiber. However, it may also be consumed with other liquids—including cow's milk, plant-based beverages, coffee, tea, water, or natural juice—without altering its properties. The formulation can be taken hot, cold, or warm.

The first daily dose should be consumed upon waking, ideally 30–60 minutes before breakfast. The second dose should be taken in the afternoon, approximately two hours before sleep, regardless of dinner timing.

Ethnography

Studying quality of life (QoL) in families with a member diagnosed with Autism Spectrum Disorders (ASD), Attention Deficit Disorder (ADD/ADHD), or Trisomy 21 (Down Syndrome) is a central aspect of this research. Such analysis makes it possible to assess not only the progress of participants undergoing nutritional intervention but also the broader impact on family dynamics.

In recent years, QoL has gained increasing importance due to the limited opportunities for social, family, and leisure activities, particularly in households managing neurodevelopmental conditions. Evidence from the initial phases of this line of research has demonstrated that nutritional interventions can strengthen specific abilities in individuals with disabilities while also enhancing the overall well-being of their families.

These outcomes justify expanding the scope of investigation from ethnographic exploration to sociological analysis, providing valuable insights into the cognitive and behavioral evolution of participants, as well as the adaptive changes within their families over the course of one year.

Sleep Physiology

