autism, and 30–45 indicate Asperger's syndrome (Martos & Morueco, 2007; García-López & Narbona, 2014b). The mean IDEA score for this sample was 63 ± 18 (Table 2).

Diagnostic (DSM-IV)	IDEA (Autism Spectrum Inventory)
ASD N = 27	Classic Kanner Autism (70–96) – 40%
Pervasive Developmental Disorders (PDD):	“Regressive Autism” (50–70) – 40%
Autistic Disorder – 74%	High-Functioning Autism (40–50) – 4%
Pervasive Developmental Disorders, Not Otherwise Specified (PDD-NOS) – 26%	Asperger's Syndrome (30–45) – 16%

Table 2. Diagnosis and IDEA scores in ASD participants

For participants with Attention Deficit Disorder (ADD/ADHD), recruitment was conducted through schools specializing in this condition. Diagnosis was confirmed using the Conners' Parent Rating Scale – Revised (Long Form), which assesses behavioral and learning difficulties, psychosomatic complaints, impulsivity, hyperactivity, and anxiety (Conners, 1999). The Hyperactivity Index was applied, with scores greater than 16 for boys and 12 for girls aged 6–11 indicating clinically significant hyperactivity (Orjales Villar, 1998) (Table 3).

Check list DSM-IV	Hyperactivity Index Conners Revised Scale	
ADD N = 25	Girls (n=4) with suspected ADD (>12)	50 %
	Boys (n=21) with suspected ADD (>16)	33 %

Table 3. Conners' Scale results for ADD participants

For DS, participants came from “CTDUCA Atención Integral de Personas Down IAP” and “Integración Down IAP.” All had karyotype-confirmed diagnoses, with one case of mosaicism.

Population Segregation

Each diagnostic group was further divided into three subgroups:

- Pilot Group: Received 23 g of T-2 twice daily and followed a strict dietary intervention protocol.
- Diet Group: Followed the dietary intervention protocol without supplementation.
- Control Group: Received neither supplementation nor dietary intervention.

The study population (ages 2–35) was further stratified into subgroups A–G (3–30 years) according to developmental stages (*Figure 6: Age distribution*).

Subgroup	Lower limit	Upper limit
A	3	5
B	6	9
C	10	13
D	14	17
E	18	21
F	22	25
G	26	30

Figure 6. Population distribution by age groups

Clinical Evaluation

Clinical follow-ups included parental reports and physical examinations aimed at detecting allergies, food sensitivities, candidiasis, infections, gastrointestinal disturbances, chronic otitis media, and other recurrent conditions. A 25-item checklist was applied, covering digestive, respiratory, dermatological, and systemic indicators.

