Laboratory Studies

Laboratory support included:

- Blood count: red/white series, platelets, sedimentation.
- Blood chemistry: glucose, urea, creatinine, uric acid, lipids, triglycerides.
- C-reactive protein: marker of inflammation.
- Serum homocysteine: marker of fat metabolism and oxidative stress.
- Plasma cortisol: indicator of adrenal activity.
- Thyroid panel: T4, free T4, T3, protein-bound iodine, TSH, total cholesterol.

- Stool analyses: coprological, coproparasitoscopic (3 samples).

Some specialized biochemical analyses were conducted at The Great Plains Laboratory (Kansas, USA), led by [name], including:

- IgG Food Allergy Panel (93 foods).
- Comprehensive Organic Acid Test (65 metabolites).
- Urinary peptides from gluten and casein.

Anthropometrics

Weight, height, and BMI were measured monthly, compared against WHO growth standards (BMI-for-age) and Mexican NOM references (NOM-008-SSA2-1993; NOM-174-SSA1-1998).

Ethnography

The study adopted a longitudinal approach using the Sherlock model, combining quantitative and qualitative assessments of personal, functional, and social quality of life. Families underwent three structured interviews (baseline, mid-study, final), recorded in audio and video, with statistical and content analysis applied to results.

Neuropsychology

IDEA Inventory (ASD): Applied to establish severity, guide interventions, and assess treatment impact across 12 dimensions.

Down Syndrome: Cognitive assessments emphasized daily life skills, cognitive processes, and emotional capacities. Recommended tests were culturally and linguistically adapted (Rondal, Perera & Spiker, 2011; Edgin et al., 2010). Tools included:

- **Ages 3–6:** BATELLE developmental inventory (Newborg et al., 1998).
- **Ages 6–35:** NEUROPSI Attention and Memory (Ostrosky et al., 2003), Executive Function Battery (Flores et al., 2008, 2011), computerized neuropsychological tasks (Ostrosky et al., 2003), basic emotion recognition tasks, Barthel Index (Cid-Ruzafa & Damián-Moreno, 1997), and BRIEF executive function scale (Goia et al., 2000).

The neuropsychological evaluation was coordinated by [name] [name], with support from trained psychology interns (4–6 students).

ADD: NEUROPSI Attention and Memory (6–85 years), EDAH (for ADHD), and Conners' Scales (long parent version, 80 items) were applied.

Polysomnography and P300

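### The dosing section recommends a casein-free vehicle for T-2 but then permits cow's milk, against the protocol's own casein rationale

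*Protocol*

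**What the plan says.** Dosage and Administration sets the regimen: "Participants will be instructed to take 23 g of the T-2 investigational nutritional formulation, twice daily, dissolved in 250 ml of liquid". For people with the three study conditions, "it is recommended that the investigational formulation be prepared with Casein-free beverage, which is casein-free and enriched with probiotic fiber". The next sentence relaxes this: "it may also be consumed with other liquids—including cow's milk, plant-based beverages, coffee, tea, water, or natural juice—without altering its properties". No condition or limit is attached to the milk option, and nothing elsewhere in the protocol text withdraws it.

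The protocol's view of casein appears in two places. In the Background, under Metabolism: "The processing of complex proteins such as casein (milk) and gluten (wheat, barley, rye, oats) is disproportionately affected, leaving peptides only partially digested". That paragraph says the peptides can cross the gut and blood–brain barriers and act like opioids, and continues: "Such effects contribute to mood instability, sensory alterations, sleep disturbances, respiratory depression, reduced attention". In the Justification, under Whey Protein Concentrate, metabolic deficiencies in Down syndrome, ASD or ADD "may impair the hydrolysis of certain animal proteins (such as casein, albumin, and red meat proteins").

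Under Population Segregation, the Pilot group "Received 23 g of T-2 twice daily and followed a strict dietary intervention protocol". The Diet group follows the dietary protocol without the supplement, and Control receives neither. Laboratory Studies lists "Urinary peptides from gluten and casein" among the specialized tests.

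**The concern.** The dosing section allows, as a routine vehicle, the very food that the background names as the source of a poorly handled protein. The phrase about not altering properties concerns the product. It does not address what the milk adds to the participant's intake.

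Two things are at stake. One is coherence: the protocol links casein peptides to poor sleep, reduced attention and unstable mood, and its Objectives include better sleep quality, steadier mood and better attention. The other is the comparison. Stage II sets supplemented participants against non-supplemented ones, and only Pilot takes T-2, so whatever comes with the vehicle is bundled with T-2 in that arm.

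**Working it through.** The protocol states no figure for milk intake, so there is none to reproduce. The check is one small calculation and a comparison of sections.

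**Daily volume of vehicle.** Inputs from Dosage and Administration: 2 doses a day, 250 ml of liquid, read as per dose.

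- Neither dose in milk: 0 × 250 = 0 ml a day
- One dose in milk: 1 × 250 = 250 ml a day
- Both doses in milk: 2 × 250 = 500 ml a day

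If 250 ml were meant as the daily total, the maximum would be 250 ml. The conflict between the sections would remain.

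**Sections side by side.**

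| Section | Position on casein or milk |
|---|---|
| Metabolism | Milk named as the source of casein; casein incompletely digested in these populations; peptides linked to sleep, attention and mood problems |
| Whey Protein Concentrate | Casein hydrolysis may be impaired in all three conditions |
| Dosage and Administration, recommendation | Casein-free beverage for the study population |
| Dosage and Administration, next sentence | Cow's milk permitted, listed first |

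The first three rows agree, and the fourth departs from them.

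**What this could do to Pilot versus Diet.** Let V be the milk taken as vehicle in Pilot (0, 250 or 500 ml a day), and let P and D be the other milk drunk in Pilot and Diet. The difference in milk intake is (P + V) − D.

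- If the diet excludes milk and is otherwise followed, P = D = 0 and the difference is V, between 0 and 500 ml a day, in Pilot only. More casein would tend to raise urinary casein peptides in Pilot, which works against showing a benefit of T-2 on that test.
- If the diet allows milk, P and D are unknown. Vehicle milk may simply replace milk drunk at other times, and no systematic difference need follow.

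The text does not say which case applies. The only diet it names is gluten-free, as an example under Family Seminars. Stage I plans a single nutritional scheme for all populations without giving its content. The share of participants using milk and its casein content are not stated either, so intake cannot be turned into a change in peptides.

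**The case against.** The strongest reply is that the casein-free beverage remains the recommendation and milk is only a tolerated fallback, which is a pragmatic choice for a population starting at age 2. The list of liquids could also be read as a note on product compatibility, since it sits in the Justification after the ingredient descriptions. If the strict diet bars milk, Pilot participants would not choose it, and the permission might never operate. The whey section, moreover, says only that hydrolysis may be impaired.

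Part of this stands. Whether milk would be used in practice cannot be settled, and no effect on any result is shown. But the sentence appears under the dosing heading, directly after a recommendation addressed to the study population, and it is a permission. A fallback does not need milk, because water, juice and plant-based beverages are already listed.

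A second reply is that T-2 itself contains milk-derived whey, minerals and lactoferrin. The protocol draws its own line here: it lists casein among the problem proteins and presents the whey as well absorbed and free of allergenic risk. On that distinction, whey in the product does not excuse casein in the vehicle.

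A reader might infer three stronger points, none of which the document supports.

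- That a written casein-free rule is broken. No such rule is stated for the diet.
- That milk as vehicle would bias the trial in favour of T-2, or distort sleep and attention by a definable amount. The likely direction on casein peptides is towards masking, and no size can be derived. Urinary peptides are also tied to no stated objective.
- That the absence of a log of the liquid used is an error. That is operational detail, and Stage I already plans to document dietary findings.

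**Conclusion.** The concern holds as an internal inconsistency of minor severity. The dosing section recommends a casein-free vehicle for the study population and then permits cow's milk, against the rationale in Metabolism and Whey Protein Concentrate.

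The exposure is at most 500 ml of milk a day per Pilot participant, assuming 250 ml is the volume per dose and both doses are taken in milk. Any consequence for Pilot versus Diet is conditional. If the diet excludes milk, vehicle milk could add casein in Pilot alone, raise urinary casein peptides and hide a benefit. If the diet allows milk, there may be no systematic difference. The wording conflict is certain; its effect on results is unknown.

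**What to change.** Delete cow's milk from the permitted liquids in Dosage and Administration, and turn the recommendation into a requirement for a casein-free vehicle: water, juice or a plant-based beverage. Coffee and tea need no change for this point if taken without milk.

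Preferably, the vehicle should carry no added probiotic fiber unless the Diet group receives the same beverage. The recommended beverage is proposed only as the T-2 vehicle, and dysbiosis is a named indicator in the Objectives, so the added fiber would be better kept out of the contrast or given to both arms. This is a preference; the text does not say whether Diet participants may use the beverage.

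The cost is a small wording change and slightly less choice for families. Several palatable options remain for young participants.

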This project represents the first biomedical protocol in Mexico to investigate neuro-nutrition—defined as dietary intervention combined with nutritional enrichment—in populations with Autism Spectrum Disorders (ASD) and Attention Deficit Disorder (ADD/ADHD), while also expanding upon the findings previously obtained in the first stage of this protocol with individuals with Trisomy 21 (Down Syndrome).

The primary aim is to provide both quantitative and qualitative evidence that disability in individuals with DS, ASD, and ADD extends beyond intellectual impairment into biological domains.

The project further seeks to enhance understanding of the metabolic and physiological characteristics of these populations, thereby informing the design of appropriate therapeutic management strategies.

Finally, it intends to demonstrate that ADD encompasses neurobiological, electrical, and biochemical processes, extending beyond the psychosocial dimensions traditionally emphasized.

METHODOLOGY

Operational Duration

The project will run for a period of 13 months.

Population Description

The estimated total population is 72 individuals between 2 and 35 years of age, divided into three groups based on their neurodevelopmental condition:

- Trisomy 21 (Down Syndrome, DS)
- Autism Spectrum Disorder (ASD)
- Attention Deficit Disorder (ADD)

Each group included between 24 and 27 participants, with more males than females. Ages ranged from 2–33 years for ASD, 2–30 years for DS, and 5–14 years for ADD. Mean ages and BMI values are shown in Table 1.

Participants	ASD (N = 27)	ADD (N = 25)	DS (N = 24)
	Mean (SD)	Mean (SD)	Mean (SD)
Age (years)	2-33 11.51±8.5	5-14 8.8±2.32	2-30 13.7±7.25
Body mass index (kg/m ²)	19.11±3.71	18.41±4.01	21.92±6.27
Men	24	20	14
Women	3	5	10

Table 1. Characteristics of each group

For participants with Autism Spectrum Disorders (ASD), recruitment was conducted at DOMUS Instituto de Autismo A.C., where diagnoses were confirmed using DSM-IV criteria (First et al., 2002). Symptom severity was assessed with the IDEA (Inventario del Espectro Autista-Autism Spectrum Inventory), which evaluates 12 developmental dimensions across four areas and is scored on a scale from 0 to 8. Scores between 70–96 indicate classic Kanner autism, 50–70 correspond to regressive autism, 40–50 reflect high-functioning

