- Lic. [name] – Project Administrator (CONACYT CVU: 499625)
- I.B. [name] – Biomedical Area Leader (CONACYT CVU: 353604)
- [name] [name] – Neurobiology Area Leader (CONACYT CVU: 39694)
- [name] [name] – Neuropsychological Evaluation for Down Syndrome (CONACYT CVU: 174346)
- Lic. [name] – Neuropsychological Evaluation for ADD (CONACYT CVU: 510484)
- [name] – Ethnographic Area Leader (CONACYT CVU: 510634)

Institutional Site

Instituto Mexicano de Medicina Integral de Sueño

Associated Entities

- Mexico: Olarte y Akle Bacteriólogos, S.A. de C.V.
- United States: The Great Plains Laboratory, Inc.

- Integración Down, I.A.P.
- Domus Instituto de Autismo

PROGRESS CONTROL PLAN

The project is scheduled to last 13 months, from December 2021 to December 2022, and will be divided into two stages of approximately six months each.

Stage I: Design and Intellectual Property Protection

Duration: First Semester

Objectives:

- Confirm the physiological and metabolic similarities documented in the literature across the study populations and design a unified nutritional intervention scheme.
- Determine expected cerebral modifications resulting from the intervention by standardizing the protocol in neurotypical animal models.

Goals:

- Create a homogeneous information base documenting physiological and metabolic affinities among the target populations.
- Obtain audiovisual records of families highlighting quality of life aspects.
- Establish a specialized dataset on sleep habits of individuals with the studied neurodevelopmental disorders.
- Document neuropsychological and behavioral profiles within family, social, and school contexts.

Activities:

- **Bimonthly 1:** Confirm study populations (Down Syndrome, ASD, ADD).
- Assign dietary subgroups (Pilot, Diet, Control).
- Conduct studies of the T-2 investigational nutritional formulation
- Baseline studies including laboratory tests, clinical reviews, anthropometric measures, ethnographic interviews, neuropsychological tests, full polysomnographic records, and P300 potentials.

- Standardize animal model protocol.
- **Month 1:** Start nutritional intervention (diet implementation).
- **Month 4-6:** Report baseline results, documenting biomedical, dietary, familial, cognitive, behavioral, and sleep-related findings. Conduct behavioral tests in animal models.

Expected Results at the End of Stage I (6 months):

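### The stated primary aim concerns the conditions themselves, but every arm is made up of diagnosed participants and most biological measures have no named norm; the Stage I comparison across diagnoses is confounded by age and sex.

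*Protocol*

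**What the plan says.** The protocol uses the word primary for one aim only, in the section on the project's contribution to advancing knowledge: "The primary aim is to provide both quantitative and qualitative evidence that disability in individuals with DS, ASD, and ADD extends beyond intellectual impairment", reaching into biological domains. The same section closes with a companion aim for ADD: "it intends to demonstrate that ADD encompasses neurobiological, electrical, and biochemical processes".

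Under Population Description, the sample is "divided into three groups based on their neurodevelopmental condition": DS, ASD and ADD. Under Population Segregation, "Each diagnostic group was further divided into three subgroups", namely Pilot, Diet and Control. The last is defined as follows: "Control Group: Received neither supplementation nor dietary intervention". Control therefore means untreated people with the same diagnosis. The only neurotypical subjects mentioned, under Stage I, are animals.

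Stage I of the Progress Control Plan has this objective: "Confirm the physiological and metabolic similarities documented in the literature across the study populations and design a unified nutritional intervention scheme". On age, Population Description says: "Ages ranged from 2–33 years for ASD, 2–30 years for DS, and 5–14 years for ADD".

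The Hypothesis, the Objectives and the Stage II goals concern something else: what changes under diet and T-2, with supplemented set against non-supplemented groups.

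**The concern.** To show that a condition involves biological abnormality, the values of affected people must be set against those of unaffected people or against stated norms. A contrast of treated with untreated patients shows what the treatment does. It does not show whether the patients' baseline biology was abnormal. If the aim stays as worded, a treatment difference, or a similarity among the three patient groups, could be read as evidence that the disability is biological, which the planned contrasts cannot show.

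The Stage I objective raises a separate problem. It compares diagnoses, but the groups differ in age and sex. Many of the planned measures, such as sleep architecture, hormones and blood chemistry, can be expected to vary with age. A difference between diagnoses may then be an age or sex difference, and a real difference may be hidden.

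**Working it through.** The protocol gives no alpha, power, effect size or margin for these aims, so there is no planned figure to reproduce. The check has two parts.

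**1. Which comparators exist?** Table 1 lists 27 ASD + 25 ADD + 24 DS = 76 participants (the text estimates 72; the difference does not matter here). All have a diagnosis, so 0 of 76 are unaffected. External references by domain:

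| Domain | Reference named |
|---|---|
| Weight, height, BMI | WHO BMI-for-age and Mexican NOM references |
| Polysomnography | International standards, which may mean scoring rules or norms; the comparator named is control groups, and the only ones defined are untreated patients |
| Blood count and chemistry, CRP, homocysteine, cortisol, thyroid panel | None |
| IgG panel, organic acids, urinary peptides | None |
| P300 | None |

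P300 is the measure closest to the electrical part of the ADD aim, and it has no reference.

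**2. How far apart are the diagnoses?** Inputs from Table 1, age as mean (SD): ASD 11.51 (8.5), n = 27; ADD 8.8 (2.32), n = 25; DS 13.7 (7.25), n = 24.

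Standardized mean difference (SMD) = difference / √((SD₁² + SD₂²)/2):

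- ADD v DS: 13.7 − 8.8 = 4.9 years; √((2.32² + 7.25²)/2) = 5.38; SMD 4.9/5.38 = 0.91. Welch 95% CI 1.7 to 8.1 years, p = 0.004.
- ASD v ADD: 11.51 − 8.8 = 2.71 years; SMD 0.43; CI −0.8 to 6.2, p = 0.12.
- ASD v DS: 13.7 − 11.51 = 2.19 years; SMD 0.28; CI −2.2 to 6.6, p = 0.33.

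Spread differs more than the means do. The ratio of age variance to that of ADD is (8.5/2.32)² = 13.4 for ASD and (7.25/2.32)² = 9.8 for DS. The range shared by all three groups is 5–14 years. If ages were normal (an assumption; they are probably skewed), about 38% of ASD and 48% of DS participants would be older than 14.

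Male share from Table 1: ASD 24/27 = 89%, ADD 20/25 = 80%, DS 14/24 = 58% (chi-square p = 0.033). Table 3 gives 21 boys and 4 girls for ADD, which would be 21/25 = 84%; the contrast with DS remains.

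How much could age alone produce? Suppose a marker has within-group correlation r with age, and take the pooled within-group age SD of 6.64 years. The difference that age induces between ADD and DS, in marker SDs, is r × 4.9/6.64. This gives 0.15, 0.30 and 0.44 for assumed r of 0.2, 0.4 and 0.6.

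**The case against.** The strongest reply is that the aim sentence stands in a section on contribution to knowledge, while the Hypothesis, Objectives and Stage II goals all concern the intervention. For those, an untreated control with the same diagnosis is the proper comparator. That is right, and the intervention comparison is not in question. But the sentence is the only aim called primary, and a statistical analysis plan cannot mend a mismatch between the protocol's aim and its population.

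A reader might infer more than the document supports:

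- *That the Stage I objective also needs an unaffected group.* It does not. It asks whether the three populations resemble one another closely enough for one nutritional scheme. An unaffected group would be needed only to show that a shared feature is peculiar to these conditions, which the objective does not ask.
- *That the biological aims cannot be addressed at all.* Reference intervals would give a norm-referenced answer with the same participants. Norms are already named for BMI and perhaps for sleep. Some findings, such as parasites in stool or the apnea–hypopnea index, carry meaning without a control arm.
- *That all three diagnoses differ widely in age.* ADD and DS do. ASD and DS have similar means (SMD 0.28) and similar ranges.
- *That the aim would be declared met whatever the data show.* The protocol states no success rule for it, and baseline values mostly within reference intervals would count against it.

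The protocol also defines age bands A to G, and age adjustment is ordinary content for an analysis plan. The bands are not tied to comparing diagnoses, however, and E to G (18–30 years) can contain no ADD participant.

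**Conclusion.** The concern holds for the stated primary aim and the ADD aim. No participant is unaffected, and no norm is named for the laboratory or P300 measures, so none of the treatment contrasts in the plan can support a claim about the conditions themselves. The Stage I comparison is answerable in principle but confounded: by age, mainly ADD against DS (4.9 years, SMD 0.91) and in the much narrower spread of ADD, and by sex (89%, 80% and 58% male).

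This rests on the Table 1 summaries and on reading Control as defined under Population Segregation. The size of the bias in any one marker depends on its relation to age, which the protocol does not give. The point limits what the trial may conclude about the conditions. It does not weaken the comparison of diet and of diet plus T-2 with no intervention.

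**What to change.** 1. Reword the aim in the contribution section so that it matches the Objectives and the Stage II goals: the effect of diet, and of diet plus T-2, in participants with each diagnosis.
2. Limit the biological statements, including the one on ADD, to a descriptive baseline profile. For each diagnosis, report the share of laboratory and sleep values outside age-specific reference intervals, and name the source of those intervals. Make no claim of abnormality for a measure without norms, such as P300 if none exist.
3. Keep the Stage I comparison across diagnoses, label it descriptive, and take age and sex into account. Adjustment and restriction to the shared 5–14 year range are both acceptable. If age is restricted, sex still has to be shown or adjusted for.

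This needs protocol wording and one baseline table, with no new recruitment or visits. The headline claim becomes narrower and the comparisons across diagnoses less precise. Under the same rough normal assumption, 22% of ASD and 12% of DS participants would be younger than 5. Restriction would then keep about 39% of 27 ≈ 11 ASD and 40% of 24 ≈ 10 DS participants, beside all 25 with ADD.
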